1.0 Introduction and Background

Screening for colorectal cancer is widely recommended but underused. Colorectal cancer (CRC) screening is cost-effective and reduces both CRC mortality and incidence by detecting and removing pre-cancerous polyps.^{1–4} Regular screening for CRC beginning at age 45 is widely recommended by several groups, including the United States Preventive Services Task Force.^{5–7} Nonetheless, over 30% of Americans are unscreened.⁸

Screening rates are even lower among underserved populations, contributing to health disparities.^{9,10} Individuals who are Black, Hispanic/Latinx, have less education, limited income, or rural residences are less likely to be screened, and thus more likely to present with advanced-stage CRC and die from it.^{11–16} Limited health literacy, which affects over 33% of American adults, further interferes with patients' ability to access and use health information.^{17–21}

Our mPATH™ (mobile PAtient Technology for Health) digital health navigator program overcomes the multilevel barriers to CRC screening. Barriers to CRC screening include patient factors (lack of knowledge, low self-efficacy, fears, negative attitudes)^{23–29} and provider/system factors (lack of time, failure to offer screening options, lack of patient support).^{30–34} mPATH™ addresses these barriers by determining if patients are due for screening, educating patients about screening options, and letting patients request a test directly via the program. mPATH™ also sends patients supportive text messages to help them complete their chosen test.

In a rigorous randomized controlled trial of 450 patients, an iPad version of mPATH™ for CRC screening (mPATH™-CRC) doubled CRC screening rates in a population prone to health disparities and was well accepted.^{35–37} Patients used mPATH™-CRC immediately before a scheduled primary care visit at one of six community-based practices. Compared to patients randomized to usual care, twice as many patients completed a CRC screening test (30% vs 15%, $p=0.0001$).³⁵ Patients in this study faced significant barriers to care; over 50% reported annual household incomes less than \$20,000 and over one-third had limited health literacy. Almost all patients rated the user-friendliness of the program as "excellent"(82%) or "good"(16%).³⁶

Incorporating patient decision aids like mPATH™ in clinical care is challenging. We are currently conducting a hybrid implementation-effectiveness study of the mPATH™-CRC iPad app in which office staff hand mPATH™ to patients as part of routine care. As of August 2022, mPATH™ has identified over 3600 patients who are overdue for CRC screening, but nursing staff have given the mPATH™-CRC app to less than 20% of these patients, resulting in tremendous missed opportunities. While our implementation study is still ongoing, we have already identified several important variables (time pressures, staff turnover, and the COVID19 pandemic) significantly hampering clinics' ability to implement mPATH™.

Delivering mPATH™ to patients at home on their own devices via the cloud is a promising strategy. Over 90% of American adults have internet access at home, including 85% who own a smartphone.³⁸ While home broadband access shows a digital divide, smartphone ownership is similar across racial/ethnic groups.³⁸ Even among rural residents, those with a high school education or less, and individuals with annual household incomes less than \$30,000, smartphone ownership exceeds 75%.³⁸ The growing ownership of smartphone and tablet devices offers new opportunities to reach broadly into patient populations. We previously

developed and pilot tested a cloud-based version of mPATH™ for lung cancer (mPATH™-Lung). In a highly pragmatic feasibility study, we sent 1000 patients electronic invitations to use mPATH™-Lung, and 41% (410) visited the mPATH™-Lung Web App and 85% of all visitors (365) completed the program. Therefore, a cloud-based version of mPATH™-CRC has great potential to reach patients and increase CRC screening independent of a medical visit, which is especially important for the 15% of adults who have not seen a doctor in the last year.³⁹ We hypothesize that at least 25% of patients who are overdue for CRC screening and use a cloud-based version of mPATH™-CRC will request a screening test via the program, demonstrating the feasibility of this strategy.

2.0 Objectives

2.1 Primary Objective

2.1.1 Evaluate the feasibility of the cloud-based version of mPATH-CRC in a large health system.

2.2 Exploratory Objective

2.2.1 Examine the response rates to different versions of the outreach invitation messages created with community member input.

3.0 Study Population

3.1 Inclusion Criteria

3.1.1 Meet the U.S. Preventive Services Task Force (USPSTF) criteria for colorectal cancer screening.

3.1.1.1 Age 45 to 75 years.

3.1.1.2 No record of current colorectal cancer screening.

3.1.2 Have a cell phone number listed in the electronic health record.

3.1.3 Language preference of English in the electronic health record.

3.2 Exclusion Criteria

3.2.1 Prior diagnosis of colorectal cancer.

3.2.2 Prior diagnosis of inflammatory bowel disease.

3.2.3 Have a record of completing a colonoscopy within the last 10 years, a FIT-DNA test in the last 3 years, or a FIT in the last 1 year based on the electronic health record.

3.2.4 Patients who may be inappropriate candidates for colorectal screening based on comorbidities (electronic Charlson Comorbidity Index > 2).

3.3 Inclusion of Women and Minorities

Participants of all races and ethnicities who meet the above-described eligibility criteria are eligible to participate in this study.

Based on WFBCCC population estimates, we expect approximately 55% of participants to be women. We will oversample for non-white patients with the goal of creating a final study sample that is approximately 50% non-Hispanic white, at least 20% Black, and at least 20% Hispanic/Latinx. We anticipate 2% or less of our sample will identify as American Indian, Asian, Hawaiian/Pacific Islanders, or more than one race, reflecting the low prevalence of these races/ethnicities in the health system's older patient population. Translating this to our sample size estimate of 240, we plan to enroll at least 132 women. Similarly, we expect approximately 20% of study participants to be Hispanic/Latino (N = 48). We plan to enroll at least 20% Black or African American (N = 48), 2% or less will be American Indian, Asian, Hawaiian/Pacific Islanders, or more than one race (N = 4). Should we not meet or exceed these estimates, the PI will engage the Office of Cancer Health Equity to discuss strategies to enhance recruitment in these target populations.

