5.0 Methods for Pragmatic Trial

5.1 Participant Recruitment

We will request a waiver of informed consent from the Wake Forest IRB to allow our highly pragmatic testing since the mPATH™-CRC web application delivers guideline recommended care and not experimental care.

Each week we will query the EHR to randomly select 240 potentially eligible patients who have no record of current CRC screening. We will oversample by race and ethnicity. We will then randomize these 240 patients, to receive one of four outreach messages with equal probability.

Patients will receive the invitation message as a HIPAA-compliant text message. Each invitation message includes an embedded hyperlink to the web app appended with an anonymous study identifier that allows us to track who visits mPATH™. A reminder message will be sent once weekly for two weeks (no more than 3 messages total). We will continue to send weekly outreach messages until 120 patients who are overdue for CRC screening complete the mPATH™-CRC web app.

Low socioeconomic status individuals are more likely to suffer health disparities from colorectal cancer. Therefore, it is critically important to include low income participants in colorectal cancer screening studies. To avoid coercion, participant incentives will not exceed \$50.

5.2 mPATH™-CRC Intervention

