7.0 Analytic Plan

7.1 Sample Size and Power

We will consider that the cloud-based mPATH™-CRC program is feasible for increasing CRC screening uptake if at least 25% of patients who complete the app request a screening test via

the program. We chose 25% as our threshold because we acknowledge that patients may not complete screening tests they request. If only half of patients complete their requested test (which is what we observed in our prior trial), a 25% test-request rate would increase overall screening rates by 12.5%, a clinically meaningful effect for a low cost intervention.

In our ongoing study of the iPad-version of mPATH™-CRC, 38% of patients who complete the program are requesting a screening test. Conservatively assuming the actual rate of requesting a screening test in the cloud-based version is 30%, a sample size of 120 patients will result in a 90% probability of demonstrating feasibility by observing a rate of at least 25%. Therefore, messages will be sent until 120 patients have completed the app in order to evaluate feasibility. Full operating characteristics of this feasibility design for a sample size of 120 are included in table below.

Table. Feasibility operating characteristics for a sample size of 120

True Rate of Requesting a Screening Test	Probability of Demonstrating Feasibility
10%	<0.001
15%	0.003
20%	0.107
25%	0.535
30%	0.904
35%	0.993
40%	>0.999

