In our ongoing trial of the iPad version of mPATH™, 50% of patients who have no record of current CRC screening in the EHR report current screening in the mPATH™ app. Based on this experience, we will conservatively estimate that 25% of patients will respond to our invitations and 50% of patients who use mPATH™ will meet our inclusion criteria of being due for CRC screening (with no risk factors) resulting in an overall weekly accrual rate of 30 patients (25% x 50% x 240). Therefore, while the sample size for our main feasibility outcome of screening decisions is 120 patients, approximately 1000 (250 per message) patients will receive an invitation for our exploratory analysis of message response rates. With a sample size of 250, the proportion who use the web app can be estimated to +/- 6.4% based on a 95% confidence interval. Based on oversampling for race/ethnicity, we anticipate that at least 50 patients from each race/ethnicity group will receive each message. With a sample size of 50, the proportion who use the web app can be estimated to +/- 14.5% based on a 95% confidence interval. The precision estimates are based on a 50% response rate as this gives the maximum half-width of a confidence interval, and therefore provides the most conservative estimate around precision.

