7.3 Analysis of Exploratory Outcome

Use of the web app will be defined as completing the web app's eligibility questions for CRC screening. For each of the four messages, we will calculate the proportion who use the web app

with a 95% confidence interval. We will also calculate the proportion who use the web app with a 95% confidence interval separately for each race/ethnic group for each of the four messages. We will assess for differences in response rates between messages using chi-square tests or Fisher's exact tests as appropriate. All tests will be 2-sided with a significance level of 0.05.

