7.4 Estimated Accrual Rate

Based on our ongoing trial experience, we will conservatively estimate that 25% of patients will respond to our invitations and 50% of patients who use mPATH will meet our inclusion criteria of being due for CRC screening without any risk factors resulting in an overall weekly accrual rate of 30 patients (25% x 50% x 240). We plan to closely monitor the accrual rate and will discontinue sending messages once 120 patients have used the app.

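### Do the section 3.3 enrolment counts, built on 240 patients, conflict with the study sizes of 120 and about 1,000 in section 7.1?

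*Combined protocol and SAP*

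**What the plan says.** Section 3.3 sets goals for the study sample as percentages: about 55% women, about half non-Hispanic white, at least 20% Black, at least 20% Hispanic/Latinx, and 2% or less from other groups. It then converts them: "Translating this to our sample size estimate of 240, we plan to enroll at least 132 women", plus 48 Hispanic/Latino, 48 Black and 4 other patients. A shortfall has one consequence: "Should we not meet or exceed these estimates, the PI will engage the Office of Cancer Health Equity" about ways to improve recruitment.

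Section 7.1 gives the study sizes. For the primary outcome, "the sample size for our main feasibility outcome of screening decisions is 120 patients", and accordingly "messages will be sent until 120 patients have completed the app in order to evaluate feasibility". For the exploratory outcome, "approximately 1000 (250 per message) patients will receive an invitation for our exploratory analysis of message response rates".

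The number 240 is defined elsewhere only as the weekly draw. In section 5.1: "Each week we will query the EHR to randomly select 240 potentially eligible patients who have no record of current CRC screening". It also appears as the multiplier in the weekly accrual formula of sections 7.1 and 7.4.

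**The concern.** Section 3.3 calls 240 a sample size estimate, and no other section does. A reader who takes the 120 completers as the enrolled sample finds a minimum of 132 women, which is more than the whole sample. A reader who takes the roughly 1,000 invited finds minority counts of about 5% where the goal is 20%. The one stated meaning of 240 is a weekly batch, which is not a final study sample.

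At stake is the monitoring of the enrolment mix. Section 3.3 words the counts as commitments and attaches an action to missing them. If the counts, and not the percentages, were the test, two people could disagree on whether it had been met: among 1,000 invited, 48 Black patients would satisfy the count at 4.8%, while among 120 completers the women's count would fail whatever the mix.

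**Working it through.** **Inputs.** Section 3.3: 55%, 20%, 20%, 2% and 240. Section 7.1: 120 completers; about 1,000 invited, 250 per message; 25% of invitees respond; 50% of users are due for screening without risk factors; at least 50 patients per race/ethnicity group per message. Section 5.1: 240 drawn per week.

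**1. The plan's own counts.** Share × 240:
- women: 0.55 × 240 = 132
- Black, and Hispanic/Latino: 0.20 × 240 = 48 each
- other: 0.02 × 240 = 4.8, stated as 4, which respects a ceiling of 2%

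The multiplication is correct.

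**2. The stated counts as shares of each possible base.**

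| Base | 132 women | 48 Black or 48 Hispanic/Latino |
|---|---|---|
| 120 completers | 110% | 40% |
| 240 | 55% | 20% |
| 1,000 invited | 13.2% | 4.8% |

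Only 240 returns the stated percentages. For comparison, the same percentages would give 66 / 24 / 24 / at most 2 on 120, and 550 / 200 / 200 / at most 20 on 1,000.

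**3. Where 240 can come from.**
- Expected app users: 120 / 0.50 = 240. Both inputs are in section 7.1.
- The same from the invited side: 120 / (0.25 × 0.50) = 960 invited, and 0.25 × 960 = 240 users. The plan speaks of about 1,000 invited, which gives 250 users.
- One weekly batch: 240, as section 5.1 states.

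The first reading agrees with the counts as a study sample and with the accrual assumptions. No section states it.

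**4. Whether the invited population is left without targets.** Section 7.1 expects at least 50 per race/ethnicity group for each of four messages: 4 × 50 = 200, and 200 / 1,000 = 20%. This is the section 3.3 percentage applied to the invited, so the two sections agree on percentages.

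**5. Whether 240 enters the design.** With feasibility claimed at 30 or more requests out of 120 (25%), the exact binomial probability P(X ≥ 30) is 0.535 at a true rate of 25%, 0.904 at 30% and 0.993 at 35%, as tabulated in section 7.1. With 240 patients and a cut-off of 60, the probability at 30% would be 0.963. The design therefore rests on 120, and the 240 of section 3.3 plays no part in it.

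**The case for a change.** The strongest case for a change is that section 3.3 makes a commitment in counts, ties an action to it, and leaves the reader to work out the denominator. The app-user reading is an inference, and the weekly batch, being the only stated meaning of 240, cannot be excluded from the text. Naming the population would take a sentence or two.

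Much of this stands. The population is unnamed, and the counts cannot describe the completers. But the percentages appear in the same paragraph, and anyone monitoring the mix can apply them to whichever group is being reported. The action is a conversation about recruitment; it is not a stopping, eligibility or analysis rule. Section 3.4 adds that trial patients are not individually registered and that their data come from retrospective chart review under a requested consent waiver, so the counts serve as planning figures.

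One might also point to section 7.4, which says the team "will discontinue sending messages once 120 patients have used the app", whereas sections 5.1 and 7.1 speak of 120 completing it. That difference in wording exists whatever the 240 means, so it neither supports nor weakens this concern.

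**Conclusion.** The concern identifies a missing label and does not show an error. The counts 132 / 48 / 48 / 4 follow correctly from 240, and 240 is the number of app users implied by section 7.1's own assumptions, provided that half of users prove due for screening. If another population was meant, the percentages still apply to it unchanged. The mismatch is large only when the counts are set against groups that section 3.3 does not name (110% or 13.2% women). Following the plan as written, the primary estimate, the 25% feasibility threshold, the operating characteristics at n = 120 and the message comparisons are all the same under every reading. The only thing that could vary is when a discussion of recruitment strategies is prompted, and the percentages are enough to guide that. Relabelling the denominator would tidy the text without changing any analysis or conclusion, so no change is called for.

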3.4 Registration Procedures

The intervention will be developed with input from focus groups. We will hold two focus groups of 8 – 12 patients each (one English speakers and one Spanish speakers) to review the animated “core content” of the video and the collected video clips of patient testimonials. We will give these participants a study information sheet explaining the purpose of the study, the nature of the data to be collected, and the voluntary nature of their participation.

[figure not shown]
After the intervention is finalized, patients will be participating in a pragmatic trial in which patient data collection will occur by retrospective electronic chart review. All patients will receive current guideline-recommended care, and we will request a waiver of patient Informed Consent. Therefore, it is impractical to register patients with the Cancer Center, and any such registration would jeopardize patient confidentiality.

4.0 Methods for Intervention Creation

4.1 Formation of Scientific and Community Advisory Committees

To ensure the intervention is culturally appropriate and addresses relevant barriers to screening, we will form a Scientific Advisory Committee and a Community Advisory Committee to guide our work. The Scientific Advisory Committee (SAC) will be comprised of nationally-known researchers with deep expertise examining and addressing barriers to CRC screening in racial and ethnic subgroups. The Community Advisory Committee (CAC) will have 6 members that include leaders of organizations that serve the Black/African American and Hispanic/LatinX communities and members of those communities. We will form the CAC in collaboration with the Wake Forest Maya Angelou Center for Health Equity and the CTSI Program in Community Engagement. Both groups have deep ties to the community. The SAC and CAC will meet at key points in the development of the revised mPATH™-CRC decision aid (**Figure 2**). At the initial meeting, the SAC and CAC will review and provide input on: 1) our outline for key content to include in the revised mPATH™-CRC decision aid, and 2) the semistructured interview guide that will be used to capture patient testimonials to ensure that appropriate questions are asked to reveal potential screening barriers and garner culturally appropriate information.

Figure 2. Overview of process for revising mPATH-CRC program

4.2 Video Testimonial Recruitment

We will query the EHR to identify patients aged 45 to 75 with a preferred language of Spanish or English who: 1) were seen at one of three Atrium Health Wake Forest Baptist primary care practices, and 2) completed a screening colonoscopy or FIT in the past 6 months. To help us recruit a diverse sample, we will abstract patient gender, race/ethnicity, age, health insurance status, preferred language, phone number, date of colonoscopy, date of FIT, screening test results. We will give the primary care providers in these three practices a list of their patients who met our EHR inclusion criteria, and we will ask the providers to nominate patients who they think may be interested in participating in a video interview. A study team member will then call the nominated patients to inform them of the study, and if interested, administer a brief eligibility questionnaire. Based on responses to the questionnaire, we will exclude patients with a history of CRC or inflammatory bowel disease.

Our goal is to interview up to 18 patients, selected to reflect diversity in age, race/ethnicity, gender, and type of screening test completed. We will schedule each participant for an individual 20-30 video interview held in a private location. Interviews will be conducted in the patient's preferred language, either English or Spanish. A trained interviewer will conduct each interview using a semi-structured interview guide. We will select clips from these interviews for potential inclusion in the revised CRC video decision aid.

4.3 Focus Group Recruitment

We will query the EHR to identify patients aged 45 to 75 with a preferred language of Spanish or English who are seen at one of four Atrium Health Wake Forest Baptist primary care practices and serve a racially/ethnically and socioeconomically diverse population. We will exclude patients who have a prior diagnosis of CRC or inflammatory bowel disease. We will selectively

recruit patients by phone and patient portal messages to ensure good representation of age, gender, race, insurance status, and screening status. We plan to include between 16-24 participants in total for these focus groups.

4.4 Focus Group Sessions

A trained moderator will lead each focus group using a moderator's guide developed by the study team. Each focus group will first review the animated core content of the CRC screening video decision aid. Questions from the moderator's guide will probe to determine if any parts of the video could be improved for clarity or acceptability. Participants will then review the patient testimonial clips grouped by theme (motivators, barriers, rationale). We will ask participants to identify which testimonials they feel should be included in the final video and why. Next, each focus group will be presented with the sample outreach messages generated with the input from the Scientific Advisory Committee (SAC) and Community Advisory Committee (CAC). The moderator's guide will explore participants' reactions to the messages, content/language that is viewed favorably or unfavorably, and suggestions for improving the messages. Additionally, focus groups will be asked to suggest their own messages that would motivate others to use mPATH™. Each participant will receive a \$50 gift card. Results from the focus groups will be used to finalize the CRC screening decision aid video and outreach messages for the pragmatic trial.

The full moderator's guide will be submitted to the IRB for review and approval prior to being used.

